1.6.2. Schematic overview of the data collection & interventions

*in case of progressive disease requiring mechanical ventilator support within the first 5 days, IV sargramostim can be initiated until the 5 day period is reached. From day 6 onwards, progressive patients in the active group will have the option to receive an additional 5 days of IV sargramostim, based on the treating physician's assessment.

1.7. Study duration

The total treatment duration of the study is 10 days, and the entire study duration is 10-22 weeks to final follow up visit.

2. Rationale and background

2.1. Rationale

Sargramostim (Leukine®) is a yeast-derived recombinant humanized granulocyte-macrophage colony stimulating factor (rhuGM-CSF, sargramostim) and the only FDA approved GM-CSF (Leucine Package Insert). GM-CSF, a pleiotropic cytokine, is an important leukocyte growth factor known to play a key role in haematopoiesis, effecting the growth and maturation of multiple cell lineages as well as the functional activities of these cells in antigen presentation and cell mediated immunity (1). Since its initial FDA approval in 1991, over 500,000 patients have received Leukine®, providing extensive clinical and post-marketing data in a broad range of treated individuals - from preterm neonates to the elderly and including males and females - representing a well-characterized safety profile for Leukine®. Leukine® administered as a subcutaneous or intravenous injection is approved for six indications including use as a medical countermeasure for radiation exposure. The US Government currently holds Leukine® in the Strategic National Stockpile. Leukine® may benefit patients with beginning signs of Acute Respiratory Distress Syndrome (ARDS) due to COVID-19 Infection. GM-CSF is a critical cytokine for the health of lungs. The alveolar macrophages are dependent on GM-CSF for differentiation and normal functioning. In addition, GM-CSF is an immunomodulator that plays a critical role in host defense by promoting differentiation of dendritic cells, and stimulating antiviral immunity (2-4).

As described in detail below, it is being studied as an adjuvant therapy in the management of life-threatening infections to boost the hosts innate immune response to fight infection, reduce the risk of secondary infection, and in varied conditions to prevent infection during critical illness (5-8). In addition, it has been studied in pulmonary conditions that affect alveolar macrophages, such as autoimmune pulmonary alveolar proteinosis (“aPAP”), with beneficial outcomes (9, 10). We propose based on preclinical and clinical data and the safety data from more than 500,000 adult and pediatric patients treated with Leukine®, that patients with beginning signs of acute lung injury and/or ARDS due to COVID-19 infection be given Leukine®. ARDS due to COVID-19 carries a high mortality rate (11) and Leukine® may confer benefit by both active management of this complication as well as in prevention of secondary infections.

In animal models of postviral ARDS and mortality, GM-CSF has demonstrated immunomodulatory effects that improve the clinical response and symptoms associated with influenza and other viral respiratory infections (12-14), and represents a promising candidate for the prevention of ARDS in patients with COVID-19.

Practical Advantages of LEUKINE® for Acute Respiratory Distress due to COVID-19

Advantage	Details
Approved for use by the FDA	- 6 indications
Safe in Pediatric and Adult populations, including elderly	- Established safety profile in pediatric and adult populations, including elderly (>500,000 patients)
Available for use in the SNS plus commercial distribution	- Current approvals provide a pre-existing distribution and stockpile resource Existing formulation safe for use with Pari LC Sprint Jet and Vectura Akita 2 nebulizers - US based manufacturing of BDS and FDP
Proven effective in fighting infection/enhancing immune response	- GM-CSF modulates immune response to influenza virus and promotes viral clearance - GM-CSF activates dendritic cells and T-cells - GM-CSF improves epithelial lung repair

2.2. Background

The proposed development plan was guided by three specific considerations:

1. Supportive Scientific Rationale:

The biology and effects of GM-CSF on the lung, specifically alveolar macrophages and epithelial cells, as well its immunomodulatory activities in stimulating antiviral immunity make GM-CSF a critical cytokine for healthy pulmonary function and defence. Detailed studies have shown that GM-CSF is necessary for the maturation of alveolar macrophages from fetal monocytes and the maintenance of these cells in adulthood (1).

GM-CSF has a wide array of effects on myeloid cells. GM-CSF has been shown to be a myelopoietic growth factor that has pleiotropic effects not only in promoting the differentiation of immature precursors into polymorphonuclear neutrophils, monocytes/ macrophages and dendritic cells, but also in controlling the function of fully mature myeloid cells (15). GM-CSF is also known to reverse immunoparalysis seen in sepsis by immune activation, resulting in beneficial outcomes (5).

There is a large body of evidence generated with GM-CSF in animal studies suggesting the potential use in ARDS and infections (16). For the purpose of brevity, we will point to the data that reflects the potential value in viral lung infections and preventing secondary bacterial infections and progression to ARDS:

Halstead and colleagues demonstrated that in vivo high airway levels of GM-CSF profoundly rescue mice from lethal influenza pneumonia. While in vitro GM-CSF is canonically described as an M1-polarizing cytokine, their data demonstrated that in vivo, during influenza A virus infection, GM-CSF instead temporizes the type II interferon-induced M1 polarization of airway macrophages and reduces inflammation induced damage (12, 13). Unkel and colleagues demonstrated GM-CSF–dependent cross-talk between influenza virus infected alveolar epithelial cells and CD103+ dendritic cells is crucial for effective viral clearance and recovery from injury and thus pointing to the potential use of GM-CSF treatment in severe influenza virus pneumonia (17). Investigations have shown that GM-CSF conferred resistance to influenza in mice via alveolar phagocytes and through alveolar macrophages which became more resistant to influenza- induced apoptosis. Delivery of intranasal GM-CSF to wild-type mice also conferred resistance to influenza (18). There is evidence that inhaled GM-CSF prevents bacteremia in post influenza bacterial pneumonia primarily through locally-mediated improved lung antibacterial resistance to systemic bacteremia during influenza A viral infection (13).

Conclusions: GM-CSF confers resistance to influenza by enhancing innate immune mechanisms that depend on alveolar macrophages, which are dependent on GM-CSF for their health and normal functioning. Pulmonary delivery of this cytokine has the potential to reduce morbidity and mortality due to viral pneumonia. This is summarized in the diagram below:

[figure not shown]

Fig. 1 GM-CSF-modulated immune response to IV infection. After pulmonary IV infection GM-CSF is released from AEC II, mediated through HGF/c-Met and TGF- α /EGFR signaling. In an autocrine manner, it stimulates epithelial repair, including epithelial proliferation and barrier restoration. Innate and adaptive immunity are activated, resulting in accelerated viral clearance. Via PU.1, GM-CSF improves AM resistance, maturation, ROS production, and phagocytosis capacity, e.g., by the Fc γ R-mediated opsonophagocytosis. GM-CSF also stimulates activation and proliferation of DCs, especially CD103⁺ DCs, and T cells and enhances Ag priming and IV-specific CD8⁺ T cell recruitment. Altogether AEC GM-CSF leads to increased survival and reduced lung injury. AEC alveolar epithelial cells, Ag antigen, AM alveolar macrophage, c-Met hepatocyte growth factor receptor, DC dendritic cell, EGFR epithelial growth factor receptor, Fc γ R Fc γ receptor, GM-CSF granulocyte and macrophage colony stimulating factor, HGF hepatocyte growth factor, PU.1 transcription factor PU.1, ROS reactive oxygen species, TGF- α transcriptional growth factor α

2. Experience: Use of Leukine® has beneficial effect in the treatment of conditions that are similar to ARDS seen with COVID-19.

A small (18 patient) double blind randomized placebo controlled clinical trial of low-dose (3mcg/kg daily for 5 days) intravenous GM-CSF treatment in adult patients with severe sepsis and respiratory dysfunction, led to the conclusion that GM-CSF treatment was associated with improved gas exchange and might play a homeostatic role (6). In a phase II study, 130 patients with severe sepsis with respiratory dysfunction were randomized to GM-CSF (250mcg/m² intravenously daily for 14days) or placebo. The results showed an improvement in 28day mortality on GM-CSF; this did not reach statistical significance due to the small sample size (7).

Herold and colleagues used Leukine® by inhalation route on a compassionate basis in six patients with moderate to severe community-acquired pneumonia or ventilator-associated pneumonia ARDS who were not improving despite all measures and at least 6 days of mechanical ventilation(8). 125mcg of Leukine® were applied by Aeroneb Solo device (Covidien, Neustadt, Germany) at an interval of 48 hours. Compared to historical controls, the authors observed significant improvement in oxygenation and lung compliance with GM-CSF therapy. This resulted in improved morbidity using standard scoring systems and 4 of the six patients recovered and were discharged from the hospital. There is an ongoing study of inhaled GM-CSF across multiple centers in Germany (GI HOPE; NCT02595060) recruiting patients with diagnosis of pneumonia associated ARDS.

There is a large body of evidence of inhaled Leukine® in autoimmune pulmonary alveolar proteinosis (aPAP), which results in accumulation of surfactant in alveolar sacs with resultant hypoxia. Tazawa and colleagues conducted a phase II study of inhaled Leukine® at 9 pulmonary centers throughout Japan in patients with unremitting or progressive aPAP with hypoxia and symptoms (9). Patients received 250mcg daily by inhalation, using an LC-PLUS nebulizer with a manual interrupter valve connected to a PARI Turbo BOY compressor, for 7 days and this cycle was repeated every other week for six cycles (total 12 weeks). The treatment was well tolerated with no serious adverse events. Adverse events were reported in just 7 of the 39 patients oxygenation, radiological changes as well as symptoms. Following these results, a larger randomized phase 3 study (PAGE study) was conducted by the Japanese investigators in 12 centers. 64 patients with mild to moderate aPAP with hypoxia were randomized to receive placebo or Leukine® (33 patients) at a dose of 125mcg twice a day for 7days

followed by a week of no treatment. This two-week cycle was repeated 12 times over a period of 24 weeks. The treatment was again well tolerated with no significant differences in adverse events between the two groups. The GM-CSF treated patients had significantly improved hypoxia parameters and radiographic changes (10). This clinical experience of use of Leukine® in viral pneumonia suggests salutary effects. In addition, these studies establish the safety of inhaled Leukine® and provide evidence for activity of inhaled Leukine®.

3. Expediency: Toxicology, pharmacologic and safety data supports the immediate clinical use of Leukine® in hypoxic respiratory failure with acute lung injury leading to ARDS due to COVID-19. Investigator brochure is available and contains detailed information on toxicity.

2.3. Risk/Benefit Assessment

COVID-19 poses a very significant risk of mortality of 3-7% and this percentage rises to mortality of 20% in patients with co-morbidity (11, 19). Of all infected patients, some 15-20% develop severe respiratory symptoms necessitating hospital admission. Around 5% of infected patients will require invasive mechanical ventilation, and many of those (40-50% will die). The current world-wide pandemic of COVID-19 is putting unforeseen stress on the entire primary, secondary and tertiary medical system, leading to unseen triage of patients that potentially benefit or not from admission to ICU units when they develop respiratory failure.

GM-CSF (sargramostim, Leukine®) has been given systemically to almost 500.000 patients in the past. It is therefore a well characterized product. Inhalation of GM-CSF has also been used to treat patients with interstitial lung disease and reduced oxygen saturation (i.e. partial acute hypoxic respiratory failure) with few significant side effects above the placebo arm. The protocol is set up to give twice daily inhalation with GM-CSF, followed by intravenous administration if the patient would move to the ICU unit on mechanical ventilation.

Although GM-CSF has been given systemically and via inhalation to patients with pneumonia-associated ARDS, there are no current data on the safety profile of this drug in patients with COVID-19. Given the severity of the clinical syndrome caused by COVID-19, and the prior triage of patients before hospital admission to the COVID-19 ward, this trial will be performed in a hospital setting on a COVID-19 ward with close monitoring of vital parameters (continuous ECG, oxygen saturation, temperature, vital clinical signs), which will allow intermediate intervention should serious side effects occur. Once on the ICU unit, patients will be intensively monitored for all vital parameters, as part of the routine ICU monitoring.

There are currently no treatments directed at improving lung repair and local immunity in COVID-19 patients, and no treatment that attempt to halt the progression from manageable acute hypoxic respiratory failure to ARDS. Preventing such progression to ARDS could have a huge impact on the foreseeable overflow of the ICU units. We therefore believe the benefits of administering inhaled GM-CSF treatment in early stage COVID-19 acute hypoxic respiratory failure outweighs the risks associated with a phase 4 IMP administration via a different route and unknown indication.

2.4. Limitations

There is a large number of COVID-19 infected patients that are currently being hospitalized across the globe. In just 9 days time, our COVID-19 ward at Ghent University Hospital has admitted 25 confirmed cases, of which a significant portion (50%) already fulfill eligibility criteria for the current proposed protocol. We therefore believe that given the current ascending part of the epidemiology curve, with numbers of patients rising sharply, there will be no shortage of patients that are eligible.

Partner Therapeutics has offered to give (free of charge) enough GM-CSF to treat 20 patients for a 10 day period and an additional 20 controls for 5 days (should deterioration occur). There are large

amounts of GM-CSF in the United States strategic national stockpile, so should this therapy work, there might be immediate worldwide application of a GM-CSF inhalation therapy.

3. Objectives

3.1. Primary Objectives

This is phase 4 academic, prospective, randomized, open-label, interventional study designed to investigate the efficacy of sargramostim (Leukine®) in improving oxygenation and short- and long-term outcome of COVID-19 patients with acute hypoxic respiratory failure. There are currently no treatments directed at improving lung repair and local immunity in COVID-19 patients, and no treatment that attempt to halt the progression from manageable acute hypoxic respiratory failure to ARDS in patients with COVID-19 infection.

Justification for our objective is that preventing progression from early acute hypoxic respiratory failure to ARDS could have a huge impact on the foreseeable overflow of the ICU units, that is already happening in some countries and is bound to happen on a global scale. The outcome of our study could thus have large impact from a medical, ethical and economic perspective.

The **hypothesis of the proposed intervention** is that GM-CSF has profound effects on antiviral immunity, can provide the stimulus to restore immune homeostasis in the lung with acute lung injury post COVID-19, and can promote lung repair mechanisms, that lead to a 25% improvement in lung oxygenation parameters.

This hypothesis is based on experiments performed in mice showing that GM-CSF treatment can prevent mortality and prevent ARDS in mice with post-viral acute lung injury.

To address our hypothesis, we will randomize patients with confirmed COVID-19 with acute hypoxic respiratory failure (saturation below 93% on minimal 2 l/min O₂ or PaO₂/FiO₂ <350) to receive sargramostim 125mcg twice daily for 5 days as a nebulized inhalation on top of standard of care (active group), or to receive standard of care treatment (control group). Upon progression of disease requiring initiation of non-invasive or invasive mechanical ventilatory support within the 5 day period, in patients in the active group, inhaled sargramostim will be replaced by intravenous sargramostim 125mcg/m² body surface area once daily until the 5 day period is reached.

To measure the effectiveness of sargramostim on restoring lung homeostasis, the **primary endpoint** of this intervention is **measuring oxygenation** after 5 DAYS of inhaled (and intravenous) treatment through assessment of pretreatment and post-treatment ratio of PaO₂/FiO₂ and through measurement of the P(A-a)O₂ gradient, which can easily be performed in the setting of clinical observation of patients admitted to the COVID -19 ward or ICU COVID-19 unit. During the 5 day treatment period, we will perform daily measurements of oxygen saturation (pulse oximetry) in relation to FiO₂, and the slope of alterations in these parameters could also be an indicator that our hypothesis is correct.

Comparison will be between active group A receiving sargramostim on top of standard of care and control group B receiving standard of care.

Data from the Wuhan COVID-19 epidemic show that patients that deteriorate are facing a prolonged period of mechanical ventilation. Therefore, from day 6 onwards, progressive patients in the active group will have the option to receive an additional 5 days of IV sargramostim, based on the treating physician's assessment. This group will be called group C. In the control group, for patients with

progressive disease requiring (non-) invasive mechanical ventilatory support, from day 6 onwards, the treating physician will have the option to initiate IV sargramostim 125mcg/m² body surface area once daily for 5 days. This group will be called group D. Comparisons of Group A (early 5 day intervention with sargramostim) with Group D (late 5 day intervention with sargramostim) will also be very informative.

3.2. Secondary Objectives

- to study if early intervention with sargramostim is safe (number of AEs/SAEs)
- to study if early intervention with inhaled sargramostim affects clinical outcome defined by
 Duration of hospital stay
 Mean and median change in 6-point ordinal scale between day 1 and day 6
 Mean and median change in clinical sign score between day 1 and day 6
 Time to clinical sign score <6 maintained for 24h
 Mean and median change of SOFA score between day 1 and day 6 or between day 1 and day 10.
 Mean and median change NEWS2 score between day 1 and day 6 or between day 1 and day 10.
 Time to NEWS2 score less than 2 for at least 24h
- to study if early intervention with sargramostim affects the rate of nosocomial infection
- to study if early intervention with inhaled sargramostim affects progression to mechanical ventilation and/or ARDS
- to study if treatment with sargramostim affects all cause mortality rate at 28 days and 20 weeks post inclusion
- to study if treatment with sargramostim affects features of secondary haemophagocytic lymphohistiocytosis, as defined by Hs score (temp, organomegaly, cytopenia, triglycerides, fibrinogen, ferritin, AST and known immunosuppression)
- to study if treatment with sargramostim has a favourable effect on long term 10-20 week follow up

4. End Points + Time Points

4.1. Primary End Points + Time Points

To measure the effectiveness of sargramostim on restoring lung homeostasis, the **primary endpoint** of this intervention is **measuring oxygenation** after 5 DAYS of inhaled (and intravenous) treatment through assessment of pretreatment (day 0) and post-treatment (day 5) ratio of PaO₂/FiO₂ and through measurement of the P(A-a)O₂ gradient, which can easily be performed in the setting of clinical observation of patients admitted to the COVID -19 ward or ICU COVID-19 unit. Preferentially, this measurement should be done in the upright position, while breathing room air for a minimum of 3 minutes. If this is impossible due to need for supplemental oxygen, FiO₂ and oxygen supplementation method should be recorded in patient record, so that A-a gradient can be normalized for age expected normal A-a gradient while on supplemental oxygen use.

During the 5 day treatment period, we will perform daily measurements of oxygen saturation (pulse oximetry) in relation to FiO₂, and the slope of alterations in this parameters could also be an indicator that our hypothesis is correct.

If the patient leaves hospital prior to the day 6 analysis point, oxygenation at day of discharge will be used as value for measuring primary endpoint.

Improvement will be expressed as % of patients showing an improvement in $P(A-a)O_2$ gradient and PaO_2/FiO_2 ratio between day 6 and day 1 of at least 25%; at least 33% and at least 50% in each treatment arm and expressed also as mean and median change in $P(A-a)O_2$ gradient and PaO_2/FiO_2 ratio comparing D6 to D1 in both treatment arms.

4.2. Secondary End Points + Time Points

- to study if early intervention with sargramostim is safe (number of AEs/SAEs)

Although sargramostim has been given previously by inhalation to patients with ARDS and interstitial lung disease, data on safety in patients with COVID-19 infection are currently lacking. Since we are randomizing against 5 days of no sargramostim treatment, comparison of AEs and SAEs between group A and group B will be very informative.

-to study if early intervention with inhaled sargramostim affects clinical outcome defined by Length of hospital stay

Mean and median change in 6-point ordinal scale change between day 1, day 6

Mean and median change in clinical sign score between day 1 and day 6

Time to clinical sign score <6 maintained for 24h

Mean and median change of SOFA score between day 1 and day 6 or between day 1 and day 10.

Mean and median change NEWS2 score between day 1 and day 6 or between day 1 and day 10.

Time to NEWS2 score less than 2 for at least 24h

- to study if early intervention with sargramostim affects the rate of nosocomial infection

Patients with viral respiratory infection are at risk of secondary bacterial infections. As part of routine clinical care, sputum samples will be collected in patients suspected of secondary bacterial pneumonia, and checked for the presence of bacteria.

-to study if early intervention with inhaled sargramostim affects progression to mechanical ventilation and/or ARDS

Decreasing oxygenation often leads to the need for non-invasive or invasive mechanical ventilation, and if severe enough to a diagnosis of ARDS. We will therefore as a secondary endpoint also study if early intervention with inhaled sargramostim prevents progression to criteria-defined ARDS (according to the American-European Consensus Conference (AECC) diagnostic criteria for ARDS: acute onset; ratio of partial pressure of arterial oxygen to fraction of inspired oxygen (PaO_2/FiO_2) of 200 or less, regardless of positive end-expiratory pressure; bilateral infiltrates seen on frontal chest radiograph; and pulmonary artery wedge pressure of 18 mm Hg or less when measured, or no clinical evidence of left atrial hypertension), requiring high-flow oxygen devices, non-invasive mechanical ventilation, mechanical ventilation, by measuring the day from admission when this diagnosis is made or therapies are initiated.

-to study if treatment with sargramostim affects all-cause mortality rate at 4 and 20 weeks post inclusion.

-to study if treatment with sargramostim affects features of secondary haemophagocytic lymphohistiocytosis.

A large subset of patients with severe COVID-19 developing respiratory failure might have a cytokine storm syndrome, designated as secondary haemophagocytic lymphohistiocytosis (sHLH). sHLH is an under-recognised, hyperinflammatory syndrome characterised by a fulminant and fatal hypercytokinemia with multi-organ failure. Cardinal features of sHLH include unremitting fever,

cytopenias, and hyperferritinaemia; hypertriglyceridemia, pulmonary involvement can present as ARDS. A cytokine profile resembling sHLH is associated with COVID-19 disease severity, characterised by increased interleukin (IL)-2, IL-7, granulocyte-colony stimulating factor, interferon- γ inducible protein 10, monocyte chemoattractant protein 1, macrophage inflammatory protein 1- α , and tumour necrosis factor- α .

Predictors of fatality from a recent retrospective, multicentre study of 150 confirmed COVID-19 cases in Wuhan, China, included elevated ferritin (mean 1297.6 ng/ml in non-survivors vs 614.0 ng/ml in survivors; $p < 0.001$) and IL-6 ($p < 0.0001$), suggesting that mortality might be due to virally driven hyperinflammation.

To address the effect of sargramostim treatment on sHLH, we will measure levels of ferritin, these chemokines and cytokines at the beginning of the trial day 0 and after the initial 5 day treatment. PBO including leukocytes and lymphocytes are performed on a routine clinical basis in these patients.

- to study if treatment with sargramostim has a favourable effect on long term 10-20 week follow up

At 10-20 weeks after Day 1, patients will be seen on routine check-up by pulmonologist, who will perform a clinical exam, pulmonary function tests (including FVC, TLC and diffusion capacity), a laboratory (ferritin, lymphocytes, leukocytes) and a 6 minutes walk test and HRCT if done per standard of care.

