6.1. Inclusion Criteria

The following patients will be enrolled

Recent (≤ 2 weeks prior to randomization) - Confident COVID-19 diagnosis confirmed by antigen detection test and/or PCR and/or positive serology, or any emerging and validated diagnostic laboratory test for COVID-19 within this period.

-In some patients, it may be impossible to get a confident laboratory confirmation of COVID-19 diagnosis after 24h of hospital admission because viral load is low and/or problems with diagnostic sensitivity. In those cases, in absence of an alternative diagnosis, and with highly suspect bilateral ground glass opacities on recent (< 24 h) chest-CT scan (confirmed by a radiologist and pulmonary physician as probable COVID-19), a patient can be enrolled as probable COVID-19 infected. In all cases, this needs confirmation by later seroconversion.

-Presence of acute hypoxic respiratory failure defined as (either or both)
saturation below 93% on minimal 2 l/min O₂
PaO₂/FiO₂ below 350

-Admitted to specialized COVID-19 ward

-Age 18-80

-Male or Female

-Willing to provide informed consent

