6.2. Exclusion Criteria

-Patients with known history of serious allergic reactions, including anaphylaxis, to human granulocyte-macrophage colony stimulating factor such as sargramostim, yeast-derived products, or any component of the product.

-mechanical ventilation before start of study

-Patients enrolled in another investigational drug study

-Pregnant or breastfeeding females (all female subjects regardless of childbearing potential status must have negative pregnancy test at screening)

- patients with peripheral white blood cell count above 25.000 per microliter and/or active myeloid malignancy

-patients on high dose systemic steroids (> 20 mg methylprednisolone or equivalent) for COVID-19 unrelated disorder

-patients on lithium carbonate therapy

-Patients with serum ferritin > 2000 mcg/L (which will exclude ongoing HLH)

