7.1.2. Withdrawal and replacement of subjects

Subjects are free to withdraw from participation in the study at any time upon request.

An investigator may discontinue or withdraw a subject from the study for the following reasons:

- allergic reactions (anaphylactic shock) to sargramostim
- Pregnancy
- Progression to non-invasive or invasive mechanical ventilation and/or ARDS between screening and randomization
- Significant study intervention non-compliance
- If any clinical adverse event (AE), laboratory abnormality, or other medical condition or situation occurs such that continued participation in the study would not be in the best interest of the subject
- If the subject meets an exclusion criterion (either newly developed or not previously recognized) that precludes further study participation

In all cases, the reason why subjects are withdrawn must be recorded in detail in the eCRF and in the subject's medical records.

If a patient decides to leave hospital before day 6 of the study, for example because of clinical improvement, the oxygenation parameters at day of discharge will be used to calculate the primary endpoint measurement.

The following actions must be taken if a subject fails to return to the clinic for a required study visit (visit at 10-20 weeks after Day 1) :

- The site will attempt to contact the subject and reschedule the missed visit within 4 weeks and counsel the subject on the importance of maintaining the assigned visit schedule and ascertain if the subject wishes to and/or should continue in the study.
- Before a subject is deemed lost to follow-up, the investigator or designee will make every effort to regain contact with the subject (where possible, 3 telephone calls and, if necessary, a certified letter to the subject's last known mailing address or local equivalent methods). These contact attempts should be documented in the subject's medical record or study file.
- Should the subject continue to be unreachable, he or she will be considered to have withdrawn from the study with a primary reason of lost to follow-up.

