7.3. Screening

Patients will be informed about the study by the treating physician.

After receiving full explanation, having received sufficient time to consider the trial, asking questions and receiving satisfying responses to all questions, patients will be asked to sign ICF.

A serum pregnancy test will be done (female patients only).

Medical history will be checked for review of exclusion criteria and relevant subject information.

Patients will be continuously monitored on the COVID-19 ward.

Exams (standard of care) include, but are not limited to:

- ECG
- Chest X-Ray, and CT-scan
- Laboratory tests for leukocyte formula, kidney and liver function, ferritin levels
- Vital signs
- Pulse oximetry, Arterial blood gas, capnography

As soon as all in- and exclusion criteria are checked and patient is considered eligible, patient can be randomized. There is no minimal window to randomize the patient.

8. Investigational Medicinal Product (IMP)

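### Progression to ARDS or respiratory support is dated from admission and can already be present at entry, which attenuates this secondary endpoint

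*Protocol*

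**What the plan says.** Section 4.2 makes progression to ARDS and respiratory support a secondary endpoint.

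- **Event.** The ARDS part uses the AECC criteria, with a PaO2/FiO2 ratio "of 200 or less, regardless of positive end-expiratory pressure; bilateral infiltrates seen on frontal chest radiograph". The sentence continues with "requiring high-flow oxygen devices, non-invasive mechanical ventilation, mechanical ventilation".
- **Clock.** The endpoint is assessed "by measuring the day from admission when this diagnosis is made or therapies are initiated".
- **Other clocks.** The Section 9.4 schedule puts randomisation on D1. Section 4.2 counts mortality from inclusion, and Section 12.2 takes the oxygenation baseline at Day 1.
- **Entry.** Section 6.1 accepts "PaO₂/FiO₂ below 350" or low saturation on supplemental oxygen, with no lower bound on the ratio. The exclusion in Section 6.2 that overlaps the event is "mechanical ventilation before start of study". Neither ARDS nor high-flow oxygen is excluded.
- **Partial safeguard.** Section 7.1.2 lists "Progression to non-invasive or invasive mechanical ventilation and/or ARDS between screening and randomization" among the reasons for which an investigator may withdraw a subject.

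**The concern.** A randomised comparison of progression should count what happens after allocation. Here the origin precedes allocation, and part of the event range lies inside the eligible range. A patient who enters with a ratio of 180 and bilateral infiltrates, or already on high-flow oxygen, has an event day before any treatment was assigned. Such events occur at the same expected rate in both arms and cannot respond to treatment. They raise both event rates and shrink the contrast.

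The endpoint is secondary, but Sections 3.1 and 5.1 justify the trial by the prospect of preventing progression to ARDS. A null result caused by events present at entry would be read as evidence against that aim.

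**Working it through.** **1. The protocol's own figure.** Section 7.1.1 expects about 30% of patients to deteriorate: 0.30 × 40 = 12 per arm, as stated. That estimate concerns ventilation (ventilation or ARDS for the control group). It does not cover high-flow oxygen, so using it for the whole composite is an assumption.

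**2. Overlap of event and eligibility.** The ARDS threshold is PaO2 ≤ 200 × FiO2 and the entry threshold is PaO2 < 350 × FiO2. With FiO2 values from the Section 9.2 table:

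| FiO2 | PaO2 giving a ratio ≤ 200 | PaO2 giving a ratio < 350 |
|---|---|---|
| 28% | ≤ 56 mmHg | < 98 mmHg |
| 40% | ≤ 80 mmHg | < 140 mmHg |
| 60% | ≤ 120 mmHg | < 210 mmHg |
| 95% | ≤ 190 mmHg | < 332.5 mmHg |

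The ARDS oxygenation range lies wholly inside the eligible range. Section 6.1 also requires bilateral opacities on CT for patients enrolled as probable cases, so the imaging criterion will often be met in that group.

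**3. Effect of counting events present at entry.** Let q be the share already meeting the event (not given in the protocol; 0 to 40% assumed). Assume new events in 30% of control and 15% of active patients who are event-free at entry. Observed rates are then

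p(control) = q + (1 − q) × 0.30 and p(active) = q + (1 − q) × 0.15.

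Power for n per arm at two-sided 0.05, with d the rate difference and p̄ the mean rate, is

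Φ{[d − 1.96 √(2p̄(1 − p̄)/n)] / √([p₁(1 − p₁) + p₂(1 − p₂)]/n)}.

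For q = 0 and n = 40 this is Φ[(0.150 − 1.96 × 0.0934)/0.0919] = Φ(−0.36) = 36%.

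| q | Control | Active | Risk ratio | Power, all 40 per arm | Power, event-free patients only (n per arm) |
|---|---|---|---|---|---|
| 0 | 30.0% | 15.0% | 0.50 | 36% | 36% (40) |
| 10% | 37.0% | 23.5% | 0.64 | 26% | 33% (36) |
| 20% | 44.0% | 32.0% | 0.73 | 20% | 30% (32) |
| 40% | 58.0% | 49.0% | 0.85 | 12% | 23% (24) |

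In the last column the risk ratio stays at 0.50. That column drops anyone with any component at entry. A component-by-component rule would keep such patients at risk of later ventilation, which is not modelled here.

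**4. Effect of the clock alone.** A log-rank simulation used 1,500 trials per scenario, a 28-day horizon and an admission-to-randomisation delay uniform over 0–4 or 0–14 days (assumed). The true hazard ratio was ln 0.85 / ln 0.70 ≈ 0.46.

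- q = 0: the estimated hazard ratio is 0.46–0.47 and power about 37–38% from either origin.
- q = 20%: the hazard ratio is about 0.69 from admission in all patients, against 0.47–0.48 from randomisation in event-free patients.
- q = 40%: 0.82–0.83 against 0.47.
- No treatment effect: the admission-based test rejects in 4.3–5.7% of trials across all scenarios.

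The attenuation therefore comes from events present at entry and not from the choice of origin.

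**The case against.** **Immortal time.** A reader might infer that the interval from admission to randomisation creates immortal-time bias, or that a chance imbalance in delay would pass for a drug effect. The documents do not support either. The delay is fixed before allocation, so randomisation balances it in expectation. Chance imbalance is already covered by the test level. The simulation shows no change in hazard ratio, power or type I error from the origin alone. Nor does Section 7.3 show a long delay: "There is no minimal window to randomize the patient" allows immediate randomisation. The firmer evidence of a gap is Section 6.1, where probable cases enter only when laboratory confirmation is still lacking after 24 hours in hospital.

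**Plain meaning of progression.** The protocol never says that a state present at entry counts as an event, and initiation of a therapy suggests something new. This has weight, and baseline-positive handling could sit in the SAP. But Section 4.2 itself fixes a clock that gives a valid day to anything arising between admission and Day 1. Its wording therefore admits these events, and nothing in the section removes them.

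**Section 7.1.2.** The withdrawal rule helps with ARDS that develops between screening and randomisation. It is optional, does not reach ARDS already present at screening, and does not mention high-flow oxygen.

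**AND or OR.** The ARDS sentence can be read as requiring both ARDS and a therapy. On that reading the patient at 180 without a device has no event at entry. The affected group is then smaller but not empty, since a patient with ARDS on high-flow oxygen remains eligible. The later wording about diagnosis or therapies favours OR, but the text does not settle it.

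**Existing alternative.** Change in the 6-point ordinal scale from Day 1 to Day 6 is already anchored at Day 1. It is a useful complement but does not repair this endpoint.

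**Conclusion.** The point stands as one of attenuation in a secondary endpoint. Section 4.2 dates progression from before randomisation, and eligible patients can already meet the ARDS or high-flow component. Counting those events moves an assumed risk ratio of 0.50 to 0.64, 0.73 or 0.85 when 10%, 20% or 40% are affected.

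These sizes rest on assumptions: the share affected, the halving of new events, and the use of 30% as the control rate. The overlap between entry criteria and event definition follows from the text alone. Power is low even with nobody affected (36%), so the correction protects the estimate more than it rescues the test.

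The admission clock by itself distorts absolute event times and is out of line with the other endpoints. It should not be read as favouring either arm or inflating type I error. The primary endpoint is unaffected.

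**What to change.** Amend Section 4.2, and carry the same definition into the SAP:

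1. Measure time from randomisation (Day 1).
2. Count only components new since Day 1: ARDS in patients who did not meet it at Day 1, and high-flow oxygen in those not on it at Day 1.
3. State whether ARDS and the listed therapies are joined by AND or OR.
4. Report the number meeting each component at Day 1, by arm, as baseline data.

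Handling of death as a competing event can be left to the SAP.

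The cost is a wording change. The Day 1 blood gas, screening imaging and the ordinal scale (whose category 3 includes high-flow oxygen) are already planned in Sections 7.3 and 9.4. Eligibility and treatment are untouched. The drawback is fewer events for the ARDS and high-flow components.
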